11.4.2 Derived PK Parameters

The derived pharmacokinetic parameters of plasma AX-158 will be determined from the individual concentration versus time data using WinNonlin Phoenix v8.3 or higher. The actual time of blood sample will be used in the calculation of the derived PK parameters. Should the actual time be unavailable but a blood sample was taken, the nominal time point will be assigned.

For the purpose of calculating PK parameters, BLQ values will be imputed as zero at pre-dose and set to missing for post-dose time points. If a Day 1, pre-dose result is missing, it will be imputed as zero. The following plasma AX-158 PK parameters will be calculated using standard non-compartmental methods:

Version:	3.0
Document Title:	SAP Template - Phase 1
Document Number:	TEMP-00109
Previous Document Number:	STATt008

Part A:

Pharmacokinetic Parameter and Unit	Definition	Computation	WinNonlin Parameter Name
C_{max} ($\mu\text{g/mL}$)	Maximum concentration.	Maximum observed concentration, occurring at T_{max} . If not unique, then the first maximum is used.	Cmax
T_{max} (h)	The time to maximum observed concentration.	Time of maximum observed concentration. If the maximum observed concentration is not unique, then the first maximum is used.	Tmax
λ_z (1/h)	Elimination rate constant.	First order rate constant associated with the terminal (log-linear) portion of the curve. Estimated by linear regression of time vs. log concentration; the regression analysis should contain data from at least 3 different time points in the terminal phase	lambda_z
$t_{1/2}$ (h)	Terminal elimination half-life.	$= \ln(2) / \lambda_z$	HL_Lambda_z
AUC_{0-24} ($\text{h}^*\mu\text{g/mL}$)	Area under the concentration-time curve (AUC) from the time of dosing to 24 h post-dose	AUC measured from the concentration at time of dosing to 24 hours post dose. The AUC is computed using the linear up-log down trapezoidal rule.	AUC0-24
AUC_{0-t} ($\text{h}^*\mu\text{g/mL}$)	Area under the concentration-time curve (AUC) from the time of dosing to the time of the last measurable concentration.	AUC measured from the concentration at time of dosing to the last measurable positive concentration. The AUC is computed using the linear up-log down trapezoidal rule.	AUClast
$AUC_{0-\infty}$ ($\text{h}^*\mu\text{g/mL}$)	AUC extrapolated to infinity.	AUC measured from the concentration at time of dosing extrapolated to infinity based on the last observed concentration.	AUCINF_obs

Pharmacokinetic Parameter and Unit	Definition	Computation	WinNonlin Parameter Name
		$= AUC_{0-t} + \frac{C_{lastobs}}{\lambda z}$	
AUC _{%extrap.} (%)	Percentage of AUC _{0-inf} due to extrapolation from last observed concentration to infinity.	Percentage of AUC _{0-inf} due to extrapolation from time of last measurable positive concentration to infinity. $= \frac{AUC_{0-inf} - AUC_{0-t}}{AUC_{0-inf}} \cdot 100$	AUC_%Extrap_obs
CL/F (L/h)	Apparent total body clearance, calculated as Dose / AUC _{0-inf} .	$= Dose / AUC_{0-inf}$	CL_F_obs
Vz/F (L)	Apparent Volume of Distribution during the terminal phase.	$= \frac{Dose}{\lambda z \cdot AUC_{0-inf}}$	Vz_F_obs
λz lower (listed only)	Elimination rate constant lower limit.	Lower limit on Time for values to be included in the calculation of λz	Lambda_z_lower
λz upper (listed only)	Elimination rate constant upper limit.	Upper limit on Time for values to be included in the calculation of λz	Lambda_z_upper
No. points λz (listed only)	Number of points used for elimination rate constant.	Number of points used for elimination rate constant	No_points_Lambda_z
R ² adjusted (listed only)	R ² adjusted.	Goodness of fit statistic for the terminal elimination phase, adjusted for the number of points used in the estimation of λz	Rsq_adjusted

Part B

Pharmacokinetic Parameter and Unit	Definition	Computation	WinNonlin Parameter Name
C _{max} (μg/mL)	Maximum concentration.	Maximum observed concentration, occurring at	Cmax

Pharmacokinetic Parameter and Unit	Definition	Computation	WinNonlin Parameter Name
		Tmax. If not unique, then the first maximum is used.	
T _{max} (h)	The time to maximum observed concentration.	Time of maximum observed concentration. If the maximum observed concentration is not unique, then the first maximum is used.	Tmax
T _{lag} (h)	The delay in achieving Tmax	Time of observation prior to the first observation with a measurable (non-zero) concentration.	Tlag
λ _z (1/h)	Elimination rate constant.	First order rate constant associated with the terminal (log-linear) portion of the curve. Estimated by linear regression of time vs. log concentration; the regression analysis should contain data from at least 3 different time points in the terminal phase	lambda_z
t _{1/2} (h)	Terminal elimination half-life.	= ln(2) / λ _z	HL_Lambda_z
AUC ₀₋₂₄ (h*μg/mL)	Area under the concentration-time curve (AUC) from the time of dosing to 24 h post-dose	AUC measured from the concentration at time of dosing to 24 hours post dose. The AUC is computed using the linear up-log down trapezoidal rule.	AUC0-24
AUC _{0-t} (h*μg/mL)	Area under the concentration-time curve (AUC) from the time of dosing to the time of the last measurable concentration.	AUC measured from the concentration at time of dosing to the last measurable positive concentration. The AUC is computed using the linear up-log down trapezoidal rule.	AUClast
AUC _{0-inf} (h*μg/mL)	AUC extrapolated to infinity.	AUC measured from the concentration at time of dosing extrapolated to infinity based on the last observed concentration.	AUCINF_obs

Pharmacokinetic Parameter and Unit	Definition	Computation	WinNonlin Parameter Name
		$= AUC_{0-t} + \frac{C_{lastobs}}{\lambda z}$	
AUC _{%extrap.} (%)	Percentage of AUC _{0-inf} due to extrapolation from last observed concentration to infinity.	Percentage of AUC _{0-inf} due to extrapolation from time of last measurable positive concentration to infinity. $= \frac{AUC_{0-inf} - AUC_{0-t}}{AUC_{0-inf}} \cdot 100$	AUC_%Extrap_obs
CL/F (L/h)	Apparent total body clearance, calculated as Dose / AUC _{0-inf} .	$= Dose / AUC_{0-inf}$	CL_F_obs
Vz/F (L)	Apparent Volume of Distribution during the terminal phase.	$= \frac{Dose}{\lambda z \cdot AUC_{0-inf}}$	Vz_F_obs
λz lower (listed only)	Elimination rate constant lower limit.	Lower limit on Time for values to be included in the calculation of λz	Lambda_z_lower
λz upper (listed only)	Elimination rate constant upper limit.	Upper limit on Time for values to be included in the calculation of λz	Lambda_z_upper
No. points λz (listed only)	Number of points used for elimination rate constant.	Number of points used for elimination rate constant	No_points_Lambda_z
R ² adjusted (listed only)	R ² adjusted.	Goodness of fit statistic for the terminal elimination phase, adjusted for the number of points used in the estimation of λz	Rsq_adjusted

Part C on Day 1:

Pharmacokinetic Parameter and Unit	Definition	Computation	WinNonlin Parameter Name
C_{max} ($\mu\text{g/mL}$)	Maximum concentration.	Maximum observed concentration, occurring at T_{max} . If not unique, then the first maximum is used.	Cmax
T_{max} (h)	The time to maximum observed concentration.	Time of maximum observed concentration. If the maximum observed concentration is not unique, then the first maximum is used.	Tmax
AUC_{0-24} ($\text{h}^*\mu\text{g/mL}$)	Area under the concentration-time curve (AUC) from the time of dosing to 24 h post-dose	AUC measured from the concentration at time of dosing to 24 hours post dose. The AUC is computed using the linear up-log down trapezoidal rule.	AUC0-24
$AUC_{0-\tau}$ ($\text{h}^*\mu\text{g/mL}$) (only required if non-q.d. dosing regimen)	Area under the plasma concentration-time curve (AUC) from the time of dosing to $<X>$ hours (dosing interval) after the Day $<X>$ dose.	AUC measured from the concentration at time of dosing to the concentration at $<X>$ hours. The AUC is computed using the linear up-log down trapezoidal rule.	AUC_TAU

Part C on Final Dosing Day:

Pharmacokinetic Parameter and Unit	Definition	Computation	WinNonlin Parameter Name
C_{max} ($\mu\text{g/mL}$)	Maximum concentration.	Maximum observed concentration, occurring at T_{max} . If not unique, then the first maximum is used.	Cmax
T_{max} (h)	The time to maximum observed concentration.	Time of maximum observed concentration. If the maximum observed concentration is not unique, then the first maximum is used.	Tmax

Pharmacokinetic Parameter and Unit	Definition	Computation	WinNonlin Parameter Name
λz (1/h)	Elimination rate constant.	First order rate constant associated with the terminal (log-linear) portion of the curve. Estimated by linear regression of time vs. log concentration; the regression analysis should contain data from at least 3 different time points in the terminal phase	lambda_z
$t_{1/2}$ (h)	Terminal elimination half-life.	$= \ln(2) / \lambda z$	HL_Lambda_z
AUC_{0-24} (h* μ g/mL)	Area under the concentration-time curve (AUC) from the time of dosing to 24 h post-dose	AUC measured from the concentration at time of dosing to 24 hours post dose. The AUC is computed using the linear up-log down trapezoidal rule.	AUC0-24
$AUC_{0-\tau}$ (h* μ g/mL) (only required if non-q.d. dosing regimen)	Area under the plasma concentration-time curve (AUC) from the time of dosing to 24 hours (dosing interval) after the Day 10 dose.	AUC measured from the concentration at time of dosing to the concentration at 24 hours. The AUC is computed using the linear up-log down trapezoidal rule.	AUC_TAU
AUC_{0-t} (h* μ g/mL)	Area under the concentration-time curve (AUC) from the time of dosing to the time of the last measurable concentration.	AUC measured from the concentration at time of dosing to the last measurable positive concentration. The AUC is computed using the linear up-log down trapezoidal rule.	AUClast
$AUC_{0-\infty}$ (h* μ g/mL)	AUC extrapolated to infinity.	AUC measured from the concentration at time of dosing extrapolated to infinity based on the last observed concentration. $= AUC_{0-t} + \frac{C_{lastobs}}{\lambda z}$	AUCINF_obs
$AUC_{\text{extrap.}}\ (%)$	Percentage of $AUC_{0-\infty}$ due to extrapolation from last observed	Percentage of $AUC_{0-\infty}$ due to extrapolation from time of last measurable positive concentration to infinity.	AUC_%Extrap_obs

Pharmacokinetic Parameter and Unit	Definition	Computation	WinNonlin Parameter Name
	concentration to infinity.	$= \frac{AUC_{0-inf} - AUC_{0-t}}{AUC_{0-inf}} \cdot 100$	
CL/F (L/h)	Apparent total body clearance, calculated as Dose / AUC _{0-inf} .	$= Dose / AUC_{0-inf}$	CL_F_obs
Vz/F (L)	Apparent Volume of Distribution during the terminal phase.	$= \frac{Dose}{\lambda z \cdot AUC_{0-inf}}$	Vz_F_obs
λz lower (listed only)	Elimination rate constant lower limit.	Lower limit on Time for values to be included in the calculation of λz	Lambda_z_lower
λz upper (listed only)	Elimination rate constant upper limit.	Upper limit on Time for values to be included in the calculation of λz	Lambda_z_upper
No. points λz (listed only)	Number of points used for elimination rate constant.	Number of points used for elimination rate constant	No_points_Lambda_z
R ² adjusted (listed only)	R ² adjusted.	Goodness of fit statistic for the terminal elimination phase, adjusted for the number of points used in the estimation of λz	Rsq_adjusted

The terminal elimination rate constant (λz) will be calculated by log-linear regression of the terminal portion of the concentration-time curve only where there are sufficient data i.e. at least 3 time points excluding C_{max} and adjusted R² is greater than or equal to 0.85; lower adjusted R² values may be acceptable at the discretion of the PK analyst if the elimination phase is clearly defined by the profile, values lower than 0.85 will be flagged within the data listing. If these criteria are not fulfilled, parameters dependent on k_{el} for calculation will not be reported.

The following urine PK parameters will be calculated:

Part C on Day 1 and Final Dosing Day

Pharmacokinetic Parameter and Unit	Definition	Computation	WinNonlin Parameter Name
Ae (µg)	Cumulative amount of study drug excreted in urine during a time interval.	The sum of the individual urine volume * urine concentration of study drug. $= \Sigma (\text{Concentration} \cdot \text{Volume})$	N/A (calculated using SAS)
Ae% (%)	Percentage of study drug excreted in urine during a time interval.	$= 100 \cdot Ae / \text{Dose}$	N/A (calculated using SAS)
CLR (L/h)	Renal clearance.	$= Ae / AUC_{0-t}$	N/A (calculated using SAS)

The derived urine pharmacokinetic parameters Ae, Ae%, CumAe, CumAe%, CLR will be determined from the individual urine concentration versus time data using SAS EG v8.3 or higher.

Derived PK parameters will be listed along with the points used to calculate λz (lower, upper, and number used) and coefficient of determination (R^2) adjusted. The derived PK parameters will also be summarised. The descriptive statistics presented will be N, n, arithmetic mean, geometric mean (with the exception of T_{\max}), SD, coefficient of variation (CV%), minimum, median, and maximum.

Any $AUC_{\% \text{ extrap}}$ values greater than 20% will be flagged within the data listing. In accordance with regulatory guidance, the associated data should not be excluded from analysis but if this is observed for >20% of the profiles, the validity of the study may be in question.

In the instance of a significant sample time deviation ($\geq 5\%$ of nominal time i.e. 72 min) for the 24 h PK sample, the AUC_{0-24} values will be excluded from statistical analysis, but will be calculated, included in the derived PK data listing and flagged. Where a non-significant sample time deviation (≤ 72 min) for the 24 h PK sample occurs and the terminal elimination rate constant (λz) is estimable, this will be used to estimate AUC_{0-24} . Where a non-significant sample time deviation (≤ 72 min) for the 24 h PK sample occurs and the terminal elimination rate constant (λz) is not estimable, WNL is unable to estimate AUC_{0-24} . Therefore, in order for an AUC_{0-24} value to be estimated, the actual sampling time (including bleed time deviations) at the 24 h nominal time point will be used for the partial AUC settings.

PK parameter listings will be presented using the Safety Set. PK parameter summaries will be presented using the PK Set. All PK parameter data included in listings and summaries will be presented to 3 significant figures (with the exception of CV% which will be presented to one decimal place).

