10.9 Efficacy and Safety Variables

10.9.1 Efficacy and Safety Measurements Assessed and Flow Chart

A schedule of study assessments is provided in [Table 10.9.1](#), [Table 10.9.2](#) and [Table 10.9.3](#). Simbec-Orion personnel who have been appropriately trained will carry out study procedures. Where more than 1 procedure is scheduled for the same time-point, the following order of priority will apply:

1. PK blood sampling. Blood samples collected outside of the defined deviation windows will be recorded as protocol deviations: \pm 1 minute for samples collected up to 45 minutes time-point (inclusive) and \pm 5 minutes for samples collected $>$ 45 minutes time-point.
2. Vital signs and 12-lead ECG (a window of \pm 10 min in relation to the nominal time-point is allowed).
3. Start or finish of urine collection interval (a window of \pm 10 min in relation to the nominal time-point).

All baseline assessments may be performed within the 1 h before dosing.

Table 10.9.1 Study Flow Chart – Part A Single Ascending Dose

| Visits ^{1,2} | Screening | Treatment Period | | | | | | | | | | | | | | Follow up | |
|---|----------------|------------------|----------|---|-----|------|----|----|----|----|----|----|--------------------------|--------------------------|--------------------------|-----------------------------|-----------------|
| | | In-house | | | | | | | | | | | | | | | |
| Days | Day – 28 to -2 | Day - 1 | Day 1 | | | | | | | | | | Post-Treatment 1 (Day 2) | Post-Treatment 2 (Day 3) | Post-Treatment 3 (Day 4) | 5-7 days from last IMP dose | |
| Time (h) | | | Pre-Dose | 0 | 0.5 | 0.75 | 1h | 2h | 3h | 4h | 6h | 8h | 12h | 24h | 36h | 48h | 72h |
| Informed Consent | X | | | | | | | | | | | | | | | | |
| Inclusion/Exclusion ³ | X | X | X | | | | | | | | | | | | | | |
| Demographics | X | | | | | | | | | | | | | | | | |
| Height/Weight/BMI ⁴ | X | X | | | | | | | | | | | | | | | |
| Medical History & Concurrent Conditions | X | | | | | | | | | | | | | | | | |
| Virology Tests (HIV, HBsAg, HCV) | X | | | | | | | | | | | | | | | | |
| Drug and Alcohol Screen ⁵ | X | X | | | | | | | | | | | | | | | |
| COVID-19 Test | X | | | | | | | | | | | | | | | | |
| Biochemistry | X ⁶ | X | | | | | | | | | | | X | | | X | X |
| Haematology | X | X | | | | | | | | | | | X | | | X | X |
| Urinalysis | X | X | | | | | | | | | | | X | X | | X | X |
| Coagulation ⁷ | X | X | | | | | | | | | | | X | | | X | X |
| Randomisation | | X | | | | | | | | | | | | | | | |

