4.2 SECONDARY VARIABLES

The secondary plasma pharmacokinetic (PK) endpoints for this study are as follows:

- C_{\max} Maximum observed concentration

Version: 3.0
Document Title: SAP Template - Phase 1
Document Number: TEMP-00109
Previous Document Number: STATt008

• T_{max}	Time to maximum observed concentration
• T_{lag}	The delay in achieving T_{max} (only in Part B)
• k_{el}	Elimination rate constant
• $t_{1/2}$	Terminal elimination half-life
• AUC_{0-24}	Area under the concentration-time curve (AUC) from the time of dosing to 24 hour post dose
• $AUC_{0-\tau}$	If part C dosing is not q.d.
• AUC_{0-t}	Area under the concentration-time curve (AUC) from the time of dosing to the time of the last measurable concentration
• $AUC_{0-\infty}$	AUC extrapolated to infinity
• $AUC_{\% \text{ extrapolated}}$	Residual area
• CL/F	Apparent total body clearance
• Vz/F	Apparent volume of distribution

The secondary urine PK endpoints for Part C of this study are:

• A_e	Amount and cumulative amount of dose excreted in urine over each collection interval
• $A_e\%$	% and cumulative % of dose excreted in urine over each collection interval
• CL_R	Renal clearance

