11.4 PK ANALYSES

11.4.1 Concentration Data

Plasma PK samples will be collected for the measurement of AX-158 at the following time points:

Part A:

- Day 1 pre-dose, 30 mins, 45 mins, 1h, 2h, 3h, 4h, 6h, 8h, 12h
- Day 2: 24h, 36h
- Day 3: 48h
- Day 4: 72h

Part B: For both treatment periods

- Day 1 pre-dose, 30 mins, 45 mins, 1h, 2h, 3h, 4h, 6h, 8h, 12h
- Day 2: 24h, 36h
- Day 3: 48h
- Day 4: 72h

Part C:

- Day 1 and Day 10 pre-dose, 1h, 2h, 3h, 4h, 5h, 6h, 8h, 12h
- Day 2 and Day 11: 24h, 36h
- Day 3 and Day 12: 48h
- Day 4 and Day 13: 72h
- Day 5: pre-dose
- Day 6: Pre-dose
- Day 7: Pre-dose
- Day 8: Pre-dose

Plasma AX-158 concentrations will be listed along with blood sampling times and details of any sampling time deviations and summarised for each treatment using the descriptive statistics N, n, arithmetic mean,

geometric mean, arithmetic standard deviation (SD), coefficient of variation (CV%), minimum, median and maximum.

The individual subject plasma AX-158 concentration profiles over time will be presented graphically on both linear and semi-logarithmic scales with each subject on a separate plot. For Part C, Day 1 and Final Dosing Day (Day 10) profiles will be presented on the same plot. The geometric mean plasma AX-158 concentration profiles over time will be presented graphically on both linear and semi-logarithmic scales with all treatments on the same plot, with separate plots for Day 1 and Final Dosing Day profiles for Part C.

Urine PK samples will be collected for the measurement of AX-158 at the following time intervals: pre-dose and in intervals of 0-12, 12-24, 24-48 and 48-72 h post-dose on Day 1 and Day 10.

Urine AX-158 concentrations will be listed along with urine volumes and summarised for each treatment using the descriptive statistics N, n, arithmetic mean, geometric mean, arithmetic standard deviation (SD), coefficient of variation (CV%), minimum, median and maximum.

For inclusion within the summary tables and plots, plasma and urine concentrations below the lower limit of quantification (LLOQ) will be imputed as zero at pre-dose and as LLOQ/2 for post-dose samples. They will be listed as recorded. Data reported as not reportable or no sample/result will be handled as missing (i.e. no assumption will be made about the actual concentration).

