11.4.3.1 Part B – Food Effect

Following logarithmic transformation, C_{\max} , AUC_{0-t} and AUC_{0-inf} values will be subjected to an analysis of variance (ANOVA) including fixed effects for sequence, period, treatment and subject nested within sequence. Point estimates and 90% confidence intervals will be constructed for the contrasts between treatments using the residual mean square error obtained from the ANOVA. The point and interval estimates will be back-transformed to give estimates of the ratios of the geometric LSMeans and corresponding 90% CIs. In addition, estimated geometric LSMeans and corresponding 95% CIs for each treatment and the within-subject CV% will be presented.

The geometric LSMean ratios and corresponding 90% CIs for C_{\max} AUC_{0-t} and AUC_{0-inf} will be represented graphically (a plot with error bars) with all parameters on one graph. On the same graph, points indicating individual within-subject ratios for the three PK parameters will be presented. Reference lines will be included to indicate the 80.00% and 125.00% CI thresholds.

Each treatment comparison will be analysed separately and will only include data from subjects who are included in the PK Set for the two treatments being evaluated.

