Programming note: This figure will be repeated for Part B (Food Effect) and Part C by Day (MAD), with treatment footnotes as per Table 14.1.1.1. Similar figures will be produced for Geometric Mean Plasma AX-158 Concentration-Time Curves on a Semi-Logarithmic Scale (Figure 14.4.1.2).

Version:

3.0

Document Title:

SAP Template - Phase 1

Document Number:

TEMP-00109

Previous Document Number:

STATt008

AX-158-101
Table 14.4.2.1Summary of Derived Plasma AX-158 Pharmacokinetic Parameters - Part A (SAD)
PK Set

Treatment	Summary Statistic	C _{max} (<units>)	T _{max} (<units>)	AUC _{0-t} (<units>)	AUC ₀₋₂₄ (<units>)	AUC _{0-inf} (<units>)	AUC%extrap (<units>)	t _{1/2} (<units>)	λ _z (1/h)	CL/F (<units>)	Vz/F (<units>)
Cohort <X>: AX-158 <X> mg (N=x)	n	x	x	x	x	x	x	x	x	x	x
	Mean	x.xx	x.xx	x.xx	x.xx	x.xx	x.xx	x.xx	x.xx	x.xx	x.xx
	Geo. Mean	x.xx	N/A	x.xx	x.xx	x.xx	x.xx	x.xx	x.xx	x.xx	x.xx
	SD	x.***	x.***	x.***	x.***	x.***	x.***	x.***	x.***	x.***	x.***
	CV%	x.x	x.x	x.x	x.x	x.x	x.x	x.x	x.x	x.x	x.x
	Min	x.x	x.x	x.x	x.x	x.x	x.x	x.x	x.x	x.x	x.x
	Median	x.xx	x.xx	x.xx	x.xx	x.xx	x.xx	x.xx	x.xx	x.xx	x.xx
	Max	x.x	x.x	x.x	x.x	x.x	x.x	x.x	x.x	x.x	x.x

Source Listing: 16.2.5.2; Produced: yyyy-mm-ddThh:mm - Page x of y

Treatment: single dose of AX-158 capsule or placebo in the fasted state.

Lower Limit of Quantification = xx.xx <units>. For the purposes of PK parameter calculation, BLQ values were set to zero at pre-dose and missing for post-dose time points.

N/A = Not applicable.

Programming note: This table will be repeated for Part B (Food Effect) and Part C (MAD) (for Day 1 and Day 10), with treatment footnotes as per Table 14.1.1.1.

Programming note: A similar table will be presented for Table 14.4.2.8 Summary of Derived Urine AX-158 Pharmacokinetic Data.

AX-158-101
Table 14.4.2.2
Summary of Statistical Analysis of Plasma AX-158 Dose Proportionality - Part A (SAD)
PK Set

Parameter	Geometric LSMeans (95% CI)					
	Cohort 1: AX-158 5 mg (N=X)	Cohort 2: AX-158 10 mg (N=X)	...	Cohort 5: AX-158 50 mg (N=X)	Intercept	Slope (95% CI)
C_{\max} (<units>)	x.xx (x.xx, x.xx)	x.xx (x.xx, x.xx)	...	x.xx (x.xx, x.xx)	x.***	x.*** (x.***, x.***)
AUC_{0-t} (<units>)	x.xx (x.xx, x.xx)	x.xx (x.xx, x.xx)	...	x.xx (x.xx, x.xx)	x.***	x.*** (x.***, x.***)
$AUC_{0-\infty}$ (<units>)	x.xx (x.xx, x.xx)	x.xx (x.xx, x.xx)	...	x.xx (x.xx, x.xx)	x.***	x.*** (x.***, x.***)
AUC_{0-24} (<units>)	x.xx (x.xx, x.xx)	x.xx (x.xx, x.xx)	...	x.xx (x.xx, x.xx)	x.***	x.*** (x.***, x.***)

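### Setting every post-dose BLQ value to missing fixes Part B Tlag at 0, so this endpoint cannot show a food-induced delay

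*SAP*

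**What the plan says.** SAP 4.2 lists Tlag among the secondary plasma PK endpoints and describes it as "The delay in achieving T_{max} (only in Part B"). Protocol 10.11.2 also derives it for Part B alone.

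Three rules in SAP 11.4.2 govern it:

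- **BLQ handling for derived parameters:** "BLQ values will be imputed as zero at pre-dose and set to missing for post-dose time points". No exception is made for BLQ samples taken before the first quantifiable one. The footnotes to Table 14.4.2.1 and Listing 16.2.5.2 repeat the rule.
- **Tlag computation (Part B table):** "Time of observation prior to the first observation with a measurable (non-zero) concentration".
- **Sample times:** "The actual time of blood sample will be used in the calculation of the derived PK parameters".

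The LLOQ/2 substitution in SAP 11.4.1 applies only to concentration summaries and plots. In the listings, BLQ results stay visible: "They will be listed as recorded". Protocol 10.11.8 (v4.0, the version supplied; the SAP cites v5.0) sets all BLQ values to missing for parameter calculation, also without exception.

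The food-effect model in SAP 11.4.3.1 takes only three parameters: Cmax and the AUCs to the last measurable time and to infinity. For these alone the plan is that "values will be subjected to an analysis of variance (ANOVA) including fixed effects for sequence, period, treatment and subject nested within sequence". Tlag is descriptive.

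**The concern.** The Tlag formula needs records of samples taken after dosing in which drug was not yet measurable. The BLQ rule removes exactly those records. Food effect on PK is a secondary objective and Tlag is derived only in the part that addresses it. The report would show a Tlag of 0 in both states by construction, and a reader could take that as evidence that food does not delay absorption.

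The description of Tlag is a second problem. It speaks of a delay in reaching Tmax, whereas the formula gives the time of the last sample before drug is first measurable. Tmax plays no part in it.

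**Working it through.** The plan states no Tlag figure to reproduce. The check applies the plan's rules to its own schedule.

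**Inputs**
- Part B sampling times (SAP 11.4.1): pre-dose, then 0.5, 0.75, 1, 2, 3, 4, 6, 8, 12, 24, 36, 48 and 72 h, which is 13 post-dose samples per period.
- SAP 11.4.2: pre-dose BLQ = 0; a missing Day 1 pre-dose result = 0; post-dose BLQ = missing; Tlag as quoted above.
- Nominal times are used, and a value set to missing is not counted as an observation. No LLOQ, PK model or lag is assumed.

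**Step 1: one profile.** Let sample k be the first quantifiable one, with samples 1 to k−1 BLQ. Under the SAP rule those k−1 samples drop out, the preceding record is pre-dose, and Tlag = 0. If they are kept as zeros, Tlag is the time of sample k−1 (pre-dose, at time 0, when k = 1).

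| First quantifiable sample (h) | Tlag, SAP rule (h) | Tlag, leading BLQ = 0 (h) |
|---|---|---|
| 0.5 | 0 | 0 |
| 0.75 | 0 | 0.5 |
| 1 | 0 | 0.75 |
| 2 | 0 | 1 |
| 3 | 0 | 2 |
| 4 | 0 | 3 |
| 6 | 0 | 4 |
| 8 | 0 | 6 |
| 12 | 0 | 8 |
| 24 | 0 | 12 |
| 36 | 0 | 24 |
| 48 | 0 | 36 |
| 72 | 0 | 48 |

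**Step 2: all patterns.** Each of the 13 samples can be BLQ or quantifiable, giving 2^13 = 8192 patterns. With pre-dose = 0, the SAP rule gives Tlag = 0 in 8191; the remaining all-BLQ pattern has no Tlag. No pattern gives Tlag above 0.

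**Step 3: fed against fasted.** There are 13 × 13 = 169 pairs of first quantifiable samples.
- SAP rule: the difference is non-zero in 0 of 169.
- Leading BLQ = 0: it is non-zero in 169 − 13 = 156, which is every pair where the two states differ.
- Restricted to first quantifiable samples at or before 4 h: 6 × 6 = 36 pairs, of which 36 − 6 = 30 are non-zero.

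**Example.** A participant is first quantifiable at 0.5 h fasted and 3 h fed. The SAP rule gives 0 and 0. With leading BLQ = 0 the values are 0 h and 2 h, a difference of 2 h.

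**Step 4: actual times.** Protocol 10.9.1 says "All baseline assessments may be performed within the 1 h before dosing". If the pre-dose PK sample falls in that window and its actual time enters the calculation unchanged, Tlag takes that time: −0.25 h for a sample 15 minutes before dosing, −1 h at the edge of the window. It still never exceeds 0.

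**The case against.** - **A BLQ sample set to missing might still count as an observation for Tlag.** The formula's wording does presuppose samples without a measurable concentration. But the SAP nowhere says that a value set to missing keeps its place, and its BLQ rule covers all derived parameters. The conflict is within the SAP and needs resolving there.
- **The effect is small.** This largely stands. Tlag has no stated decision role, Part B has eight participants, and a delay could still be seen in Tmax, the individual plots and the listings. The LLOQ is not given, so how often early samples will be BLQ is unknown. If every 0.5 h sample is quantifiable, nothing is lost. The pair counts weight implausibly late first samples equally with early ones, so they show only what the rule permits.
- **The BLQ rule also touches AUC.** True. It draws the first trapezoid from zero at pre-dose straight to the first quantifiable sample. If that sample is at 2 h with concentration 1, the area is 0.5 × 2 × 1 = 1.0, against 0.5 × (2 − 1) × 1 = 0.5 if the 1 h BLQ is kept as zero. That is a separate choice. A Tlag-only fix leaves it alone, at the price of handling leading BLQ values differently for Tlag and AUC, which the SAP should state openly.
- **Nothing says pre-dose samples enter at negative times.** Fair. The conclusion does not depend on Step 4.

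**Conclusion.** The concern holds. As written, Part B Tlag cannot exceed 0 in either state, and the fed-fasted difference is 0 for every possible pair of first quantifiable samples at nominal times. This follows from two rules in the same SAP section and rests only on the reading that a value set to missing is not an observation.

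The consequence is one uninformative and potentially misleading secondary endpoint. The food-effect ANOVA does not use it. It should be corrected because the plan prescribes a wrong result for a named endpoint and the repair is nearly free.

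**What to change.** 1. In SAP 11.4.2, add a rule for Part B Tlag only: post-dose BLQ values before the first quantifiable concentration are treated as zero, so their sample times count, and the pre-dose record is taken as time 0. Leave the BLQ rule for AUC and all other parameters unchanged, and say so.
2. In SAP 4.2 and 11.4.2, describe Tlag as the time of the last sample before the first quantifiable concentration. Protocol 10.11.8 (v4.0) carries the same inaccurate description.
3. Amend the BLQ footnotes of the Part B version of Table 14.4.2.1 and of Listing 16.2.5.2.
4. Add a programming note that the Part B version of Table 14.4.2.1 includes Tlag. The shell shown is the Part A one, which rightly omits it, and the existing note says only "This table will be repeated for Part B (Food Effect) and Part C (MAD) (for Day 1 and Day 10").
5. If protocol v5.0 keeps the v4.0 BLQ rule, record the exception in SAP 1.2.

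The cost is one derivation rule applied to the same profiles, two descriptions, two footnotes and a programming note, with a line in SAP 1.2 if needed. Data collection, the ANOVA and all other parameters are unaffected. The rule gives no lag information for a period with a quantifiable pre-dose value, which the PK Set allows up to 5% of Cmax. In that case the first measurable record is the pre-dose sample itself, and Tlag stays at 0 under either rule.
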